9.6. Pharmacokinetic Analysis

9.6.1. Pharmacokinetics in Plasma

Plasma concentrations of CPX-POM and its metabolites will be determined by GLP-validated liquid chromatography tandem mass spectroscopy(LC-MS/MS) assays. Analysis of resultant plasma CPX-POM (and its metabolites) concentration-time data will be performed using non-parametric PK data analysis methods using Phoenix WinNonlin 7.0 (Certara LP, Princeton, NJ). PK parameters will be listed and summarized for each analyte using descriptive statistics (e.g., sample size, arithmetic mean, % coefficient of variation, standard deviation, median, minimum, and maximum). The following PK parameters will be determined:

- C_{max} - Maximum observed plasma concentration (C_{max}) observed following administration of a single dose on Day 1
- T_{max} - Time to reach maximum observed plasma concentration (C_{max})
- $AUC_{[0-t]}$ - Area under the concentration-time curve following administration of a single dose on Day 1
- $AUC_{[t-\infty]}$ - Area under the concentration-time curve following administration of a single dose on Day 1 from the last quantifiable concentration (t) to infinity.
- AUC_{inf} - Area under the curve from time zero to extrapolated infinite time [$AUC_{(0-\infty)}$] following administration of a single dose on Day 1 as the sum of $AUC_{[0-t]} + AUC_{(t-\infty)}$
- $C_{SS_{max}}$ - Maximum observed plasma concentration at steady-state on Day 5
- $T_{SS_{max}}$ - Time to reach maximum observed plasma concentration ($C_{SS_{max}}$) on Day 5
- AUC_{SS} - Area under the concentration-time curve over the dosing interval at steady-state following drug administration on Day 5
- λ - Apparent first-order elimination rate constant
- $t_{1/2}$ - Apparent elimination half-life
- Cl_s – Systemic clearance following administration of a single dose on Day 1
- Cl_{ss} – Systemic clearance at steady-state
- V_d – Apparent volume of distribution
- V_{ss} – Steady-state volume of distribution

- C_{max} Derived Accumulation Ratio - C_{SSmax}/C_{max}
- AUC Derived Accumulation Ratio - $AUC_{ss}/AUC_{(0-\infty)}$
- CL_r – Single dose (Day 1) and steady-state (Day 5) renal clearance

Plasma drug and metabolite concentration-time data and derived plasma PK parameters will be presented in tabular and graphic format.

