| CPX-POM infusions ²⁴ | | X | X | X | X | X | | | | |

Abbreviations: ALP = alkaline phosphatase; ALT = alanine aminotransferase; aPTT = activated partial thromboplastin time; AST = aspartate aminotransferase; BSA = body surface area; BUN = blood urea nitrogen; CPX-POM = ciclopirox phosphoryloxymethyl ester; CT = computed tomography; D = day; ECG = electrocardiogram; ECOG = Eastern Cooperative Oncology Group; EDTA = ethylenediamine tetraacetic acid; eGFR = estimated glomerular filtration rate; GGT = gamma glutamyl transferase; HIV = human immunodeficiency virus; IV = intravenous; MUGA = multi-gated acquisition; MRI = magnetic resonance imaging; PBMC = peripheral blood mononuclear cell; PD = pharmacodynamic; PK = pharmacokinetic; PT = prothrombin time; RBC = red blood cell; T3 = triiodothyronine; T4 = thyroxine; TSH = thyroid stimulating hormone; V = visit; WBC = white blood cell.

1. On Days 1 and 5 of Cycle 1, patients will be required to stay at the clinical research unit for at least 12 hours for PK sampling and other assessments. If patients are unable or unwilling to attend the required 12 hours of clinic visitation required for steady-state PK sampling on Day 5 of Cycle 1, the steady-state PK sampling may be postponed to Day 5 of Cycle 2. To shorten the duration of the Cycle 1, Day 1 visit, if needed, the safety laboratory blood samples required for this visit may be drawn up to 3 days before Day 1.
2. The Day 10 (Visit 8) study visit will only be required during Cycle 1.
3. After cycle 1; visit windows can be considered on a case by case basis due to events such as holidays; Cycle 1 needs to occur without visit windows. D6 can occur +2 calendar days for cycles after Cycle 1 is completed.
4. If final treatment cycle, patient returns for assessments on Day 22. If additional cycles are planned, patient skips this visit and restarts schedule at Day 1 (except for PK). Patients may continue to receive cycles of CPX-POM until progression of disease, intolerable toxicity occurs, or another withdrawal criterion applies.

5. The Follow-up visit will occur 28±5 days after the last dose of CPX-POM administered during the last treatment cycle. Or, in the event that a patient discontinues from the study prematurely, the site will make every effort to perform the assessments listed for this study visit.
6. Hepatitis screening will include tests for Hepatitis A, Hepatitis B, and Hepatitis C.

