19. **Cycle 1:** Serial, 3-mL blood samples will be taken for determination of plasma CPX-POM and metabolites concentrations during Cycle 1 at 0.25, 0.5, 1.0, 1.5, 2.0, 3.0, 4.0, 5.0, 6.0, 8.0, 10.0, 12.0, and 24.0 hours following completion of the 10-minute IV infusion on Day 1 and on Day 5. Each PK sample should be collected as close as possible to the planned time. The 12.0 hour collection can have a +/- 1-hour window (collect within 11 to 13 hours) and the exact time must be recorded. The actual date and time of each blood sample collection will be accurately recorded.
20. **Cycle 1:** Complete 24-hour urine samples for determination of CPX-POM and metabolites concentrations, and measurement of urine volume will be obtained from each patient in urine collection and storage containers during Cycle 1. A sample will be taken at pre-dose on Day 1, and complete urine samples will be collected at 0-12 and 12-24 hour collection intervals post-dose on Days 1 and 5. The 12 hour collection can have a +/- 1-hour window (collect within 11 to 13 hours) and the exact time must be recorded.
21. **Cycle 1:** Urine β -glucuronidase activity will be determined in the complete 24-hour urine samples collected on Day 1 and Day 5 of Cycle 1.
22. 7-mL blood samples will be obtained in EDTA-containing blood collection tubes at pre-dose on Day 1 and Day 5 of each treatment cycle, and on Day 22 of the last treatment cycle. Plasma and buffy coat (PBMCs) will be isolated, transferred to storage tubes, and stored frozen.
23. BSA will be calculated by the site personnel using the Dubois method of calculation using screening height and baseline weight measurements. BSA is to be recalculated before study drug administration on Day 1 of every other treatment cycle, starting with Cycle 3 and the patient's study drug dose adjusted accordingly.
24. CPX-POM infusions will be administered once every 24 hours as 10-minute IV infusions on Days 1-5 of each 21-day treatment cycle. After completion of Cycle 1 for the first 4 to 6 patients, the SRC will review safety, PK, and PD data to determine if any changes to the dosing schedule are indicated (e.g., adding an additional 5 days of dosing to each treatment cycle).

GLOSSARY OF ABBREVIATIONS AND DEFINITION OF TERMS

| | |
|----------------------|---|
| AE | adverse event |
| ALT | alanine aminotransferase |
| ANC | absolute neutrophil count |
| aPTT | activated partial thromboplastin time |
| AST | aspartate aminotransferase |

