| AUC | area under the concentration-time curve following a single dose on Day 1 |
| AUC _{ss} | area under the concentration-time curve over the dosing interval at steady-state following drug administration on Day 14 |
| AUC _[0-t] | area under the concentration-time curve following administration of a single dose on Day 1 |
| AUC _[t-∞] | area under the concentration-time curve following administration of a single dose on Day 1 from the last quantifiable concentration (t) to infinity |
| AUC _{inf} | area under the curve from time zero to extrapolated infinite time [AUC(0 ∞)] following administration of a single dose on Day 1 as the sum of AUC[0-t] + AUC(t-∞) |
| BSA | body surface area |
| CL _r | single dose (Day 1) and steady-state (Day 14) renal clearance |
| CL _s | systemic clearance following administration of a single dose on Day 1 |
| CL _{ss} | systemic clearance at steady-state |
| C _{max} | the maximum observed serum/plasma/PBMC concentration of drug |
| C _{SSmax} | the maximum observed plasma concentration of drug and metabolites observed at steady-state over the dosing interval |
| CPX | ciclopirox |
| CPX-G | ciclopirox glucuronide |
| CPX-O | ciclopirox olamine |
| CPX-POM | ciclopirox phosphoryloxymethyl ester (ciclopirox prodrug) |
| CRF | case report form(s) |
| CRO | contract research organization |
| CT | computed tomography |
| CTCAE | Common Terminology Criteria for Adverse Events |
| DLT | dose limiting toxicity |
| ECG | electrocardiogram |
| ECOG | Eastern Cooperative Oncology Group |
| ELISA | enzyme-linked immunoassay |

| | |
|----------|--|
| FDA | (United States) Food and Drug Administration |
| GCP | Good Clinical Practice |
| GFR | glomerular filtration rate |
| GGT | gamma glutamyl transferase |
| GLP | Good Laboratory Practices |
| HNSTD | highest non-serious toxic dose |
| IB | Investigator's Brochure |
| ICF | informed consent form |
| ICH | International Council on Harmonisation |
| IL | Interleukin |
| IRB | institutional review board |
| IV | intravenous |
| LC-MS/MS | liquid chromatography tandem mass spectroscopy |
| MedDRA | Medical Dictionary for Regulatory Activities |
| MIBC | muscle invasive bladder cancer |
| mRNA | messenger RNA |
| MTD | maximum tolerated dose |
| MUGA | multi-gated acquisition |
| n | number of subjects |
| NCI | National Cancer Institute |
| NOAEL | no observed adverse effect level |
| PBMC | peripheral blood mononuclear cell |
| PD | pharmacodynamic |
| PK | pharmacokinetic |

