Scientists at the University of Kansas synthesized the phosphoryloxymethyl ester of CPX, CPX-POM to enable parenteral administration of CPX. In contrast to CPX and CPX-O, CPX-POM has high water solubility and is readily formulated for parenteral administration.

Pharmacokinetic (PK) studies in laboratory animals showed that CPX-POM is rapidly and completely metabolized to its active metabolite, CPX, which then disappears from plasma following systemic administration of CPX-POM. Following systemic administration of CPX-POM, the dose is eliminated from the body via renal clearance of CPX and the inactive glucuronide metabolite of CPX (CPX-G).

In rats, intravenous (IV) CPX-POM administered for 28 consecutive days did not cause mortality or changes in body weight, food consumption, ophthalmology, hematology, coagulation, clinical chemistry, urinalysis, or organ weights. There were no test item-related findings grossly or microscopically at the highest dose level tested (50 mg/kg/day). Test item-related transient clinical signs, including slight to moderate decreased activity, increased respiration, eating-like behavior, and slight to moderate incoordination were noted immediately after dosing at 50 mg/kg/day. The no observed adverse effect level (NOAEL) in rats was 25 mg/kg/day in males and 50 mg/kg/day in females.

In dogs, CPX-POM administered for 28 consecutive days did not cause mortality or changes in body weight, food consumption, electrocardiogram (ECG) parameters, hematology, coagulation, clinical chemistry, urinalysis, or organ weights. There were no test item-related findings grossly or microscopically at dose levels up to 30 mg/kg/day. Test item-related transient clinical signs such as salivation, fecal changes, aggression, shaking, and tremors were noted after dosing at the highest dose level tested on the study (30 mg/kg/day). Convulsion was apparent in one dog on a single occasion. Test-item related ophthalmic changes were noted in 3/10 dogs treated with 30 mg/kg/day. Thus, the NOAEL in dogs was determined to be 10 mg/kg/day and the highest non-serious toxic dose (HNSTD) in the dog was determined to be 30 mg/kg.

The starting dose of CPX-POM in patients was selected based on the results of the IV CPX-POM 28-day Good Laboratory Practices (GLP) toxicology studies conducted in the rat and dog and consistent with FDA guidance ([FDA, 2010](#)) (see Section 4.4).

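### The AUC accumulation ratio in Section 9.6.1 is 1 at steady state whatever the half-life (linear, time-invariant kinetics, equal doses), so it does not measure accumulation

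*Protocol*

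**What the plan says.** Protocol Section 9.6.1 plans two accumulation ratios for each analyte. One uses peak concentration ("Derived Accumulation Ratio - C_{SSmax}/C_{max"). The other is "AUC Derived Accumulation Ratio - $AUC_{ss}/AUC_{(0" to infinity (the quotation stops before the infinity sign). The numerator, AUCss, is defined there as "Area under the concentration-time curve over the dosing interval at steady-state following drug administration on Day 5". The denominator is the Day 1 area up to the last quantifiable concentration plus the extrapolated tail. No Day 1 area over the first dosing interval is listed by name.

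Dosing and sampling are in the footnotes to the Schedule of Assessments (Section 1.3). Footnote 24: "CPX-POM infusions will be administered once every 24 hours as 10-minute IV infusions on Days 1-5" of each cycle. Footnote 19 has plasma samples running to 12.0 "and 24.0 hours following completion of the 10-minute IV infusion on Day 1 and on Day 5". Footnote 1 adds that "the steady-state PK sampling may be postponed to Day 5 of Cycle 2".

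The glossary gives a different day for the numerator: "area under the concentration-time curve over the dosing interval at steady-state following drug administration on Day 14". It also puts steady-state renal clearance on Day 14, where Section 9.6.1 has Day 5.

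The SAP document supplied consists of table and listing shells. It lists plasma and urine concentrations (Listings 16.2.6-1 and 16.2.6-2), but has no PK-parameter table and does not redefine the ratio.

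**The concern.** An accumulation ratio should say how much larger exposure is over one dosing interval after repeated dosing than over the same interval after the first dose. Its denominator is therefore the first-interval AUC. Here the denominator is the whole single-dose AUC, which already contains the tail that later doses build on. Numerator and denominator then become the same quantity at steady state, and the ratio loses its dependence on half-life.

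Characterising PK after single and multiple dosing is a secondary objective (Section 3), and Section 9.6.3 plans to explore single versus multiple dosing as an influence on exposure. A reader of the PK table could take a ratio of 1.0 as evidence that daily exposure does not build up over five days, when the ratio would read about 1.0 whether it did or not.

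**Working it through.** The plan states no value for the ratio and no half-life, so there is no figure to reproduce. The inputs are the definitions in Section 9.6.1, a 24 h dosing interval and five doses (footnote 24). Every half-life *h* below is an assumption.

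**Step 1, superposition.** With linear, time-invariant kinetics and equal doses, the AUC over the fifth interval is the sum of single-dose areas over 0-24, 24-48, 48-72, 72-96 and 96-120 h, that is, single-dose AUC(0-120 h). At full steady state the sum runs to infinity and equals AUC(0-∞).

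**Step 2, listed ratio.** AUC(0-120)/AUC(0-∞) cannot exceed 1 under these conditions, and is exactly 1 at full steady state. For one compartment it is 1 − 2^(−120/h).

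**Step 3, accumulation.** Day 5 AUC(0-24)/Day 1 AUC(0-24) = (1 − 2^(−120/h)) / (1 − 2^(−24/h)).

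At h = 12: 1 − 2^(−10) = 0.999, and 0.999/0.75 = 1.33. At h = 24: 1 − 2^(−5) = 0.969, and 0.969/0.5 = 1.94.

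| Assumed half-life (h) | Listed ratio at dose 5 | Day 5 / Day 1 AUC(0-24) |
|---|---|---|
| 4 | 1.00 | 1.02 |
| 6 | 1.00 | 1.07 |
| 8 | 1.00 | 1.14 |
| 12 | 1.00 | 1.33 |
| 24 | 0.97 | 1.94 |
| 48 | 0.82 | 2.81 |

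At the longest half-lives the listed ratio falls as accumulation rises.

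**Step 4, other disposition models.** Take two compartments with a 0.5 h distribution phase and half of the AUC in the terminal phase. At a 12 h terminal half-life the AUC(0-24) ratio is (0.5 + 0.5 × 0.999)/(0.5 + 0.5 × 0.75) = 1.14; at 24 h it is (0.5 + 0.5 × 0.969)/(0.5 + 0.5 × 0.5) = 1.31. The listed ratio is 1.00 and 0.98, and the Cmax ratio 1.02 and 1.03, so the Cmax ratio does not always reveal the rise. For a metabolite formed with a 0.25 h half-life and eliminated with a half-life of 12 or 24 h, the AUC(0-24) ratio is 1.34 or 1.96 against a listed ratio of 1.00 or 0.97.

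**Step 5, what moves the listed ratio above 1.** For the parent, clearance is dose/AUC, so at equal dose the ratio is Day 1 clearance over steady-state clearance: 1/0.7 = 1.43 if clearance falls to 70%, and 1/0.5 = 2.0 if it falls to 50%. For a metabolite, AUC is amount formed divided by metabolite clearance, so either increased formation or reduced clearance lifts it. Noise or extrapolation error apart, a value above 1 signals time-dependent or nonlinear kinetics.

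**Step 6, the Day 1 24 h sample.** With infusions every 24 h, 24.0 h after the end of the first 10-minute infusion is the end of the second. Take a 12 h half-life and a starting concentration of 1 (bolus approximation). The concentration is 0.5 at 12 h and 0.25 at 24 h, or 1.25 if the Day 2 dose is already in. The true 12-24 h area is (0.5 − 0.25)/(ln 2/12) = 4.33. The area from the contaminated sample is 12 × (0.5 + 1.25)/2 = 10.5. True Day 1 AUC(0-24) is 0.75/(ln 2/12) = 12.98, so it is inflated by 1 + (10.5 − 4.33)/12.98 = 1.48. A corrected ratio of 1.33 would then read 1.33/1.48 = 0.90. At 24 h the inflation is 1.35 and 1.94 would read 1.44. The same sample feeds the present denominator.

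**Step 7, below-quantification values.** At 6 h, dropping the area after 12 h on Day 1 but keeping it on Day 5 gives 1.00/0.75 = 1.33 instead of 1.07. Truncating both days at 12 h returns 1.07.

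**Step 8, postponed sampling.** Cycle 2 Day 5 comes 21 days after Cycle 1 Day 5. Carry-over at half-lives up to 24 h is under 0.0001% of the interval AUC, so postponement does not alter the ratio at equal dose.

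**The case against.** The strongest reply concerns size. Section 2 reports from animal studies that "CPX-POM is rapidly and completely metabolized to its active metabolite, CPX, which then disappears from plasma". If every analyte has a half-life of 4 h or less, the two ratios differ by 2% or less. At 6 h the gap is 7% in one compartment and 3% in the two-compartment model, hardly readable in cohorts of one to six patients. This stands, and it limits the point. But the animal statement gives no half-life for CPX or its glucuronide, and Section 9.6.1 computes the ratio for each analyte.

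Second, nothing is lost. Sampling runs to 24 h on both days, AUC[0-t] is listed, and when the 24 h concentration is quantifiable that is essentially the Day 1 AUC(0-24). True, and it is why the fix is cheap; the reported parameter would still be mislabelled.

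Third, Section 9 describes itself as a summary pending the SAP, and only shells were supplied. Fuller SAP text could redefine the ratio. That cannot be excluded; the protocol definition would still need to match.

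Fourth, unequal handling of below-quantification values is unlikely where the two days' 24 h levels are close. Fair, but stating one rule for both days removes the question.

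A reader might infer more than the documents support: that the ratio will conceal material accumulation in this trial, or distort the safety committee's review of the schedule. The first needs half-lives the documents do not give. On the second, the committee reviews PK data, but nothing says it uses this ratio. Nor does a value above 1 necessarily mean that clearance has fallen; for a metabolite, greater formation has the same effect.

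**Conclusion.** The definition is wrong for its label. The result is exact under linear, time-invariant kinetics with equal doses: 1 at steady state for any half-life, below 1 when Day 5 falls short of it. It does not depend on the compartmental model.

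How much it matters depends on half-lives that have to be assumed. The difference is negligible at 4 h or less, small at 6 h, and of practical interest from about 8 to 12 h upwards. The consequence is confined to one descriptive parameter under a secondary objective. The primary objective, DLTs and MTD are untouched, and no stated decision rule uses the ratio. It is worth correcting because it costs little. The Day 14/Day 5 conflict is a separate inconsistency that the same edit should settle; it does not affect the algebra.

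**What to change.** - In Section 9.6.1, define the AUC accumulation ratio for each analyte as Day 5 AUC(0-24 h) over Day 1 AUC(0-24 h), dose-normalised if the two doses differ (for example, after a dose reduction when sampling moved to Cycle 2). Add Day 1 AUC(0-24 h) to the parameter list.
- If AUCss over AUC to infinity is kept, relabel it a time-dependence (linearity) ratio.
- In footnote 19, clarify that the Day 1 24 h sample is drawn before the Day 2 infusion.
- State how AUC(0-24 h) is obtained when the 24 h value is below quantification, with the same rule on both days: extend to 24 h with the fitted rate constant, or truncate both days at the same time.
- Reconcile Day 14 in the glossary with Day 5 in Section 9.6.1.

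The cost is a few lines in Section 9.6.1, the glossary, footnote 19 and the PK analysis specification. No samples or visits are added. The only operational item is the sampling clarification, which sites would need to be told.

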9.6.2. Pharmacokinetics in Urine

Urine concentrations of CPX-POM and its metabolites will be determined by GLP-validated LC-MS/MS assays. Urine PK parameters will be generated using non-parametric PK data analysis methods, listed, and summarized for each analyte using descriptive statistics (e.g., sample size, arithmetic mean, % coefficient of variation, standard deviation, median, minimum, and maximum). The following PK parameters will be determined:

- Mass excreted
- Excretion rate
- Cumulative mass excreted

Urine β -glucuronidase activity will be measured for each patient and summarized.

9.6.3. Covariates and Pharmacokinetics

The influence of dose, single versus multiple dose administration, β -glucuronidase activity, and other potential covariates (e.g., creatinine clearance, concomitant medications, concurrent disease) on CPX-POM and metabolite exposure will be examined in an exploratory fashion given the limited sample size.

9.7. Pharmacodynamic Analyses

The pharmacologic effects of CPX-POM on circulating Wnt and Notch cell signaling biomarkers will be characterized. Plasma concentrations of VEGF, IL-6, and IL-8 will be determined prior to, during, and following CPX-POM treatment for each cycle by ELISA. Expression of survivin; Notch receptors 1, 2, and 3; Notch ligand Jagged-1, Notch target proteins HES1, Hey1, cyclin D1, and cMyc; as well as γ -Secretase proteins Presenilin-1 and Nicastrin, will be determined in PBMCs by qRT-PCR.

Relationships between observed biomarker changes and drug and/or metabolite exposure as well as other measures will be explored using descriptive statistics, and/or additional PK/PD modeling to support the dose selection for future studies. Demographic and baseline characteristics may be included in the modeling analysis.

9.8. Interim Analyses

No formal interim analysis is planned. After each cohort is completed, an SRC comprised of the CRO Medical Monitor, Principal Investigator(s), and Sponsor representatives will meet to discuss the data and decide upon the next dose escalation. In addition, after completion of Cycle 1 for the first 4 to 6 patients, the SRC will review safety, PK, and PD data to determine if any changes to the dosing schedule are indicated.

10. REGULATORY, ETHICAL, AND STUDY OVERSIGHT CONSIDERATIONS

10.1. Regulatory and Ethical Considerations

10.1.1. Institutional Review Board/Ethics Committee

IRBs must be constituted according to the applicable state and federal requirements of each participating location including International Council on Harmonisation (ICH) Good Clinical Practice (GCP).

It is the responsibility of each investigational site to submit the protocol, IB, patient ICF, patient recruitment materials (if applicable), and other documentation as required by the IRB to their IRB for review and approval. A copy of the written approval must be provided to the sponsor or CRO. The documentation should clearly mention the approval/favorable opinion of the protocol, the patient ICF, and patient recruitment materials (if applicable), including respective version dates. The written approval and a list of the voting members, their titles or occupations, and their institutional affiliations must be obtained from the IRB(s) and provided to the sponsor or CRO prior to the release of clinical study supplies to the investigational site and commencement of the study. If any member of the IRB has direct participation in this trial, written notification regarding his or her abstinence from voting must also be obtained.

Sites must adhere to all requirements stipulated by their respective IRB. This includes notification to the IRB regarding: protocol amendments, updates to the patient informed consent, recruitment materials intended for viewing by patients, IND safety reports, serious and unexpected AEs, reports and updates regarding the ongoing review of the trial at intervals specified by the respective IRB, and submission of final study reports and summaries to IRB.

It is the responsibility of each investigational site to submit information to the appropriate IRB for annual review and annual re-approval.

